6.2 Sponsor's Termination of Study

Although TaiwanJ Pharmaceuticals has the intention of completing the study, the company reserves the right to discontinue the study at any time for clinical or administrative reasons. If \geq 30% of subjects received study treatments has a hepatic AE of $>$ Grade 3 or a non-hepatic, drug-related AE of \geq Grade 3, then the study will be terminated.

6.3 Reasons for Subject Withdrawal

Any subject may withdraw his or her consent at any time.

Subjects will be monitored carefully during the study. Any subject who experiences an increase in ALT value greater than 3X baseline during the treatment period will be monitored weekly. If ALT values increase to greater than 5X the baseline ALT will be rechecked within 48 hours and if value remains $>$ 5X baseline, the subject will be withdrawn from the study. The subject will then be followed, and ALT, AST, prothrombin time, and total bilirubin will be monitored every 2 weeks thereafter until the value that led to the subject's discontinuation of therapy has returned to the baseline value (Baseline for prothrombin time and total bilirubin is the value obtained at the screening).

Other reasons for withdrawal from the study may include, but are not limited to the following:

- Subject is in violation of the protocol, defined as refusal or inability to adhere to prescribed dosing and/or follow-up regimen.
- Subject is lost to follow-up.
- Subject experiences a serious or intolerable AE that, in the medical opinion of the principal investigator, warrants discontinuation.
- Subject has laboratory safety assessments that reveal clinically significant worsening from baseline values.
- Subject develops, during the course of the study, symptoms or conditions listed in the exclusion criteria.
- Subject requires a medication that is prohibited by the protocol.
- Investigator or TaiwanJ Pharmaceuticals requests an early discontinuation of the trial for any reason.

The investigator may also withdraw a subject upon the request of TaiwanJ Pharmaceuticals or if TaiwanJ Pharmaceuticals terminates the study. Upon occurrence of a serious or intolerable AE, the principal investigator will confer with TaiwanJ Pharmaceuticals. If a subject is discontinued because of an AE, the event will be followed until it is resolved or until the principal investigator or sub-investigator deems the event to be chronic or the subject to be stable.

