6.3.1 Handling of Withdrawals

Subjects should be encouraged to complete all study procedures; however, all subjects are free to withdraw from the study at any time. Subject participation in the trial may be stopped at any time at the discretion of the investigator or at the request of TaiwanJ Pharmaceuticals.

When a subject withdraws from the study, the reason(s) for withdrawal shall be recorded by the investigator in the source documents and on the relevant page of the CRF. Whenever possible, all subjects who withdraw from the study prematurely will undergo all end-of-study (Visit 8) and follow-up (Visit 9) assessments. Subjects who fail to return for final assessments will be contacted by the site in an attempt to have them comply with the protocol. Follow-up assessment for early withdrawals will be attempted through 2 documented telephone calls to the subject followed by 1 registered letter. All attempted contacts should be detailed thoroughly in the source documentation.

It is vital to obtain follow-up data on any subject withdrawn because of an AE or serious adverse event (SAE). In any case, every effort must be made to undertake protocol-specified safety follow-up procedures.

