8.2. Subject Exclusion Criteria

1. The presence of any of the following will exclude a subject from study enrollment: Any chronic liver disease other than NASH (i.e., drug-induced, viral hepatitis, autoimmune hepatitis, primary biliary cirrhosis, primary sclerosing cholangitis, hemochromatosis, A1AT deficiency, Wilsons disease)
2. Cirrhosis, as assessed clinically or histologically
3. Presence of vascular liver disease
4. BMI \leq 25 kg/m²
5. Excessive alcohol use ($>$ 20 g/day) within the past 2 years

6. AST or ALT > 250 U/L.
7. Type 1 diabetes mellitus
8. Bariatric surgery in the past 5 years.
9. Weight gain or weight loss of > 5% in past 6 months or > 10% change in past 12 months.
10. Contraindication to MRI
11. Inadequate venous access
12. HIV antibody positive, hepatitis B surface antigen positive (HBsAg), or HCV RNA positive.
13. Receiving an elemental diet or parenteral nutrition
14. Chronic pancreatitis or pancreatic insufficiency
15. Any history of complications of cirrhosis (i.e. ascites, hepatic encephalopathy, or portal hypertensive bleeding), even if absent or optimized with medical management at time of screening
16. Concurrent conditions:
 - a) Inflammatory bowel disease
 - b) Unstable angina, myocardial infarction, transient ischemic events, or stroke within 24 weeks of screening
 - c) Ongoing infectious, immune mediated disease within previously 1 years
 - d) Any malignant disease (other than basal cell carcinoma of the skin) within previous 2 years
 - e) Prior solid organ transplant
 - f) Any other concurrent condition which, in the opinion of the investigator, could impact adversely on the subject participating or the interpretation of the study data.
17. Concurrent medications including:
 - a) Anti-NASH therapy(s) initiated after the liver biopsy diagnosing NASH. Anti-NASH therapies include S-adenosyl methionine (SAMe), milk thistle, and vitamin E.
 - b) Antidiabetic mediation which may impact NASH histology initiated after the liver biopsy diagnosing NASH including thiazolidinediones (glitazones), dipeptidyl peptidase 4 inhibitors (gliptins) or glucagon-like peptide 1 analogs.
 - c) Immune modulatory agents including systemic steroids, methotrexate, anti-TNF- α therapies (infliximab, adalimumab, etanercept) or anti-integrin therapy (namixilab).
 - d) UGT2B7 enzyme inhibitors (e.g., diclofenac, fluconazole, medroxyprogesterone acetate, meclofenamic acid)

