 - e) UGT2B7 inducers (e.g., dexamethasone, phenobarbital, rifampicin, omeprazole)
 - f) Chronic opioid use within 28 days prior to screening (Day -28)
18. Self-reported or known marijuana or illicit drug use 30 days before the screening
19. The following laboratory abnormalities:
 - a) HbA1c > 9.0%
 - b) Neutrophil count < 1.0 x 10⁹ / L
 - c) Platelets < 100 10⁹ / L
 - d) Hemoglobin < 10 g/dl
 - e) Albumin < 3.5 g

- f) International normalized ratio (INR) > 1.3
- g) Any elevation of bilirubin above normal (unless Gilbert's syndrome or extrahepatic source as denoted by increased indirect bilirubin fraction).
- h) Serum creatinine > 1.5 mg/dl
- i) Creatinine clearance ≤ 50 ml/minute calculated by Crockroft-Gault

20. Pregnancy or breastfeeding.

21. Women, of childbearing age, who are not willing to practice effective contraception (i.e., barrier, oral contraceptives, or past medical history of hysterectomy) for the 48-week duration of the trial and for 1 month after the last administration of the drug. Women with documented (not reported) oophorectomy or hysterectomy are considered sterile. Women with tubal ligation are at small risk and should have pregnancy test at screening.

22. Participation in an investigational drug study within past 30 days.

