10. SCHEDULE OF EVENTS

10.1 Tests and Evaluations

No subject may be permitted to undergo any protocol-specified investigations or interventions in this study until they have provided a signed, dated, written informed consent.

All tests and evaluations must be performed prior to that day's administration of study drug treatment. Subjects should undergo all tests and evaluations specified in the protocol, regardless of whether they remain on study drug. Insofar as possible, all blood samples should be collected at approximately the same time of day in each visit, in order to minimize diurnal variation.

The required procedures for patient evaluation at each study visit are outlined in the study. Schedule of Visits and Procedures are in Sections 10.2 and detail items in section 10.3 through 10.4.8. Detailed instructions for specific procedures are presented in Section 11.

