10.6 Occurrence of Hepatocellular Carcinoma in Patients with NAFLD

Any liver tumor occurrence will, in all cases, be diagnosed at the site according to local standard of care practices. In the event of a suspected tumor, subjects should undergo any confirmatory investigations that may be required.

These confirmatory investigations should be performed as soon as possible and in all cases within 21 days of diagnosis. All confirmatory investigations, including any additional scans that may be required, will be the responsibility of the study site.

If, after performing any confirmatory investigations that may be required, the diagnosis of malignancy is confirmed, the subject should immediately and permanently cease administration of study drug. Subjects with confirmed malignancy may then receive any other therapies or treatment modalities that their attending physicians consider appropriate.

However, such subjects should be encouraged to remain in the study and complete all scheduled visits, evaluations and assessments as per the protocol. If the subject elects not to participate in remaining visits, they should be strongly encouraged to complete a 'premature withdrawal' visit or early discontinuation visit as detailed in Section 10.4.

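### SAP 6.2 places scheduled visits by label alone, so an early leaver's End of Treatment MRI can be analysed as Week 24 whatever day it was done

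*Protocol*

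**What the plan says.** **How subjects leave early.** Protocol 6.3 introduces its list with "Other reasons for withdrawal from the study may include, but are not limited to the following". One entry is "Subject develops, during the course of the study, symptoms or conditions listed in the exclusion criteria". Section 6.3.1 adds a general discretion: "Subject participation in the trial may be stopped at any time at the discretion of the investigator".

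**What leavers are asked to do.** Under 6.3.1, where possible, "all subjects who withdraw from the study prematurely will undergo all end-of-study (Visit 8) and follow-up (Visit 9) assessments". Section 10.4.6 asks for an End of Treatment visit with follow-up four weeks later. Section 10.8, on withdrawal of consent, places that visit at the time of withdrawal. Section 10.4.4 names the End of Treatment visit as Visit 8, sets it at Week 24 ± 4 days, and includes the liver-fat MRI.

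**What the SAP does with visits.** SAP 6.2 uses scheduled visits as labelled. An unscheduled visit can stand in for an unavailable scheduled one only if it falls within a window that runs to the halfway point towards the neighbouring scheduled visit. No day check is stated for a visit that carries a scheduled label.

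**What the SAP does with missing scans.** SAP 6.9.1 uses multiple imputation for results missing for reasons such as early termination, in the Full Analysis Set (the primary population) and the mITT population. The Per Protocol Population requires 24 weeks of completed treatment, so early leavers are not in it.

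**The concern.** The primary efficacy endpoint is change in liver fat at Week 24. The protocol gives an early leaver's exit visit the same name and number as the Week 24 visit, and the SAP then trusts the label. The same scan on the same day can therefore have two different fates, depending on how the site recorded the visit: it becomes the subject's Week 24 value, or it is set aside and Week 24 is imputed.

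These are different quantities. One is liver fat after a shorter course of treatment; the other is a model-based estimate of liver fat at Week 24. With about 20 subjects per arm, no replacement, and power estimates that make no allowance for dropout, that choice should be written into the plan and not left to data entry.

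**Working it through.** The SAP prints no window days, so there is no stated figure to reproduce. They follow from its halfway rule and the protocol's visit table.

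**Inputs (Protocol 1.1 and 10.2.1).** Visit 4 = Day 56, Visit 5 (Week 12) = Day 84, Visit 6 = Day 112, Visit 7 = Day 140, Visit 8 (Week 24) = Day 168, Visit 9 = Day 196. On-study MRIs are at Weeks 12 and 24.

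**Windows (midpoint of adjacent scheduled days).**
- Week 24: lower (140 + 168)/2 = Day 154; upper (168 + 196)/2 = Day 182.
- Week 12: lower (56 + 84)/2 = Day 70; upper (84 + 112)/2 = Day 98.
- If only MRI visits are counted, the Week 24 lower limit is (84 + 168)/2 = Day 126. SAP 6.2 speaks of scheduled visits in general, so Day 154 is the more natural reading.

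**Example: exit MRI on Day 112, no later scan.**

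| How the visit is recorded | Rule in SAP 6.2 | Week 24 value in FAS and mITT |
|---|---|---|
| Visit 8 / End of Treatment | by label, no day limit | the Day 112 scan, 168 − 112 = 56 days early |
| Unscheduled or early withdrawal | window applies | not used (154 − 112 = 42 days before the window; 126 − 112 = 14 days on the MRI-visit reading); imputed |

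**Effect of SAP 6.9.1 Step 3.** That step averages Week 12 and Week 24 to form the endpoint. If it is applied as written, the mislabelled scan carries a weight of 1/2 in the subject's endpoint; otherwise it carries full weight.

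**Leverage of one subject.** In an arm of 20, one value has weight 1/20 = 5% in the unadjusted arm mean. If the early scan differs from the value that would have been imputed by x points, the arm mean moves by x/20. Purely as an assumption, let x equal the whole target effect of about 5 in SAP 6.1: the shift is 5/20 = 0.25 per such subject, or 0.125 with the Step 3 averaging. The documents do not give x or the number of early leavers.

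**The case against.** The strongest reply is that the early scan is misused only if the exit visit is entered as scheduled Visit 8, and no document says that it will be. Section 10.4.4 defines Visit 8 as Week 24 ± 4 days. The mention of Visit 8 in 6.3.1 may describe the content of the visit and not its database label. The synopsis lists early withdrawal visits beside unscheduled ones, and 10.6 speaks of a premature withdrawal or early discontinuation visit. SAP 6.9.1 plainly expects early-termination results to be missing. All of this stands, and it limits the certainty. It does not close the gap, because the rule as written gives the wrong answer under the protocol's own name for the visit.

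A second reply is that Protocol 13.2 says values missing through early termination are not imputed, so leaving the scan out might not lead to imputation. The documents do differ here. The SAP is the later and more detailed analysis document, and 6.9.1 should govern, but this is worth stating.

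A third is that an observed scan at, say, Day 150 may be better than an imputed value. That is a fair preference, but it argues for a stated rule, not for letting the label decide.

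A reader might also infer that 6.3 itself needs rewording: that a subject who drifts past an entry limit, such as "Weight gain or weight loss of > 5% in past 6 months or > 10% change in past 12 months" or one listed under "The following laboratory abnormalities", must leave and lose the Week 24 scan. The documents do not support that.
- The 6.3 list is optional, and 6.3.1 gives the investigator the same freedom anyway.
- Section 10.1 says "Subjects should undergo all tests and evaluations specified in the protocol, regardless of whether they remain on study drug". For confirmed malignancy, 10.6 says "such subjects should be encouraged to remain in the study and complete all scheduled visits". Sections 6.1 and 10.4.4 also ask for continued follow-up, and 10.4.4 names Week 24.
- Weight loss is counselled throughout the study, so withdrawal for it is implausible.
- Several of the laboratory limits (neutrophils, platelets, haemoglobin, creatinine) are plausible safety signals on treatment, and 10.4.7 and 12.4 give no numerical limits in their place.

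**Conclusion.** The point holds as a gap in the visit-assignment rule. Under SAP 6.2, an early leaver's MRI labelled Visit 8 is analysed as Week 24 with no lower limit on its day. Labelled unscheduled and outside the window, it is not used and Week 24 is imputed. This affects the Full Analysis Set and mITT analyses but not the Per Protocol analysis.

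The conclusion rests on two things: that some subjects leave early and have an exit MRI before Day 154, and that some of those visits are recorded as Visit 8. The documents establish neither. They also give no early-leaver rate, no standard deviation for liver-fat change and no time course, so no bias or loss of power can be calculated. It would be going too far to say that early scans will be counted as Week 24, or that the primary result is biased. The effect is probably small, and the case for acting is that the correction costs almost nothing.

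**What to change.** Add to SAP 6.2, before unblinding:
- End of Treatment and early-termination assessments are assigned to visits by study day, using the existing halfway window, whatever visit label they carry. For MRI, Week 24 is Day 154 to Day 182.
- An earlier MRI is not used as Week 24. If it falls in Day 70 to Day 98 and the Week 12 scan is missing, it may serve as Week 12.
- Where no scan falls in the Week 24 window, Week 24 is missing and is imputed under SAP 6.9.1, which takes precedence over the no-imputation sentence in Protocol 13.2.

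The cost is one short SAP paragraph and a minor programming change. No protocol amendment is needed, and 6.3 and 6.3.1 can stay as they are for this purpose. The downside is that a few observed scans outside the window are not used as Week 24 values; they can still be listed.

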6.3.1 Handling of Withdrawals

Subjects should be encouraged to complete all study procedures; however, all subjects are free to withdraw from the study at any time. Subject participation in the trial may be stopped at any time at the discretion of the investigator or at the request of TaiwanJ Pharmaceuticals.

When a subject withdraws from the study, the reason(s) for withdrawal shall be recorded by the investigator in the source documents and on the relevant page of the CRF. Whenever possible, all subjects who withdraw from the study prematurely will undergo all end-of-study (Visit 8) and follow-up (Visit 9) assessments. Subjects who fail to return for final assessments will be contacted by the site in an attempt to have them comply with the protocol. Follow-up assessment for early withdrawals will be attempted through 2 documented telephone calls to the subject followed by 1 registered letter. All attempted contacts should be detailed thoroughly in the source documentation.

It is vital to obtain follow-up data on any subject withdrawn because of an AE or serious adverse event (SAE). In any case, every effort must be made to undertake protocol-specified safety follow-up procedures.

6.3.2 Replacements

Subjects who are withdrawn from the study will not be replaced.

7. STUDY POPULATION

7.1. Number of Subjects

A target of 60 subjects will be enrolled. It is envisioned that recruitment of subjects will occur at approximately 12 sites. Subjects who discontinue treatment per protocol or withdraw consent after initiating treatment will not be replaced. Any subject who fails a screening investigation may, at the discretion of the investigator, be re-tested, providing that they remain able to complete screening assessments within the protocol-specified screening period (up to 4 weeks).

7.2. Assignment of Subjects Numbers

Patients will be randomized in the order in which they are enrolled into this double-blind study by using a computer-generated randomization schedule. TaiwanJ Pharmaceuticals will prepare the schedule prior to the start of the study. This number will designate which allocated treatment a patient will receive. The randomization schedule will be a ratio of 1:1:1 to one of the following three treatment groups:

- JKB-121 5 mg tablet twice daily orally
- JKB-121 10 mg tablet twice daily orally
- Placebo as tablet twice daily orally

The patient number will be used to identify the patient throughout the duration of the study and will be used on the CRF.

8. SUBJECT SELECTION

This clinical trial can fulfill its objectives only if appropriate subjects are enrolled. The following eligibility criteria are designed to select subjects for whom protocol treatment is considered appropriate. All relevant medical and non-medical conditions should be taken into consideration when deciding whether this protocol is suitable for a particular subject.

Eligibility criteria may not be waived by the investigator and are subject to review in the case of a Good Clinical Practices (GCP) or a regulatory authority audit. Any questions regarding a subject's eligibility should be discussed with TaiwanJ site management or study management personnel (see protocol cover page) prior to enrollment.

8.1. Subject Inclusion Criteria

Subjects must meet all of the following inclusion criteria to be eligible for enrollment into the study:

1. Age \geq 18 years
2. Provision of written informed consent
3. Biopsy-proven NASH within 12 months prior to randomization as reviewed by central pathologist with:
 - NASH activity score (NAS) of 4 or more
 - 10% or more macrovesicular steatosis
 - cytologic ballooning score of at least 1 point
 - hepatic fibrosis of at least 1 point
 - hematoxylin and eosin (H&E) stained slides and/or paraffin block available for independent assessment
4. ALT $>$ 40 U/L for women and $>$ 60 U/L for men at screening and at least once in the previous 12 months.
5. MRI with $>$ 6% hepatic steatosis
6. HbA1c of \leq 9.0
7. Lipid lowering agents (i.e. statins) and allowable antidiabetic treatment (i.e. metformin or sulfonylurea) must be stable at screening and during the study.
8. Agree to use of effective contraceptive measures if female of child bearing potential.

8.2. Subject Exclusion Criteria

1. The presence of any of the following will exclude a subject from study enrollment: Any chronic liver disease other than NASH (i.e., drug-induced, viral hepatitis, autoimmune hepatitis, primary biliary cirrhosis, primary sclerosing cholangitis, hemochromatosis, A1AT deficiency, Wilsons disease)
2. Cirrhosis, as assessed clinically or histologically
3. Presence of vascular liver disease
4. BMI \leq 25 kg/m²
5. Excessive alcohol use ($>$ 20 g/day) within the past 2 years

6. AST or ALT > 250 U/L.
7. Type 1 diabetes mellitus
8. Bariatric surgery in the past 5 years.
9. Weight gain or weight loss of > 5% in past 6 months or > 10% change in past 12 months.
10. Contraindication to MRI
11. Inadequate venous access
12. HIV antibody positive, hepatitis B surface antigen positive (HBsAg), or HCV RNA positive.
13. Receiving an elemental diet or parenteral nutrition
14. Chronic pancreatitis or pancreatic insufficiency
15. Any history of complications of cirrhosis (i.e. ascites, hepatic encephalopathy, or portal hypertensive bleeding), even if absent or optimized with medical management at time of screening
16. Concurrent conditions:
 - a) Inflammatory bowel disease
 - b) Unstable angina, myocardial infarction, transient ischemic events, or stroke within 24 weeks of screening
 - c) Ongoing infectious, immune mediated disease within previously 1 years
 - d) Any malignant disease (other than basal cell carcinoma of the skin) within previous 2 years
 - e) Prior solid organ transplant
 - f) Any other concurrent condition which, in the opinion of the investigator, could impact adversely on the subject participating or the interpretation of the study data.
17. Concurrent medications including:
 - a) Anti-NASH therapy(s) initiated after the liver biopsy diagnosing NASH. Anti-NASH therapies include S-adenosyl methionine (SAMe), milk thistle, and vitamin E.
 - b) Antidiabetic mediation which may impact NASH histology initiated after the liver biopsy diagnosing NASH including thiazolidinediones (glitazones), dipeptidyl peptidase 4 inhibitors (gliptins) or glucagon-like peptide 1 analogs.
 - c) Immune modulatory agents including systemic steroids, methotrexate, anti-TNF- α therapies (infliximab, adalimumab, etanercept) or anti-integrin therapy (namixilab).
 - d) UGT2B7 enzyme inhibitors (e.g., diclofenac, fluconazole, medroxyprogesterone acetate, meclofenamic acid)
 - e) UGT2B7 inducers (e.g., dexamethasone, phenobarbital, rifampicin, omeprazole)
 - f) Chronic opioid use within 28 days prior to screening (Day -28)
18. Self-reported or known marijuana or illicit drug use 30 days before the screening
19. The following laboratory abnormalities:
 - a) HbA1c > 9.0%
 - b) Neutrophil count < 1.0 x 10⁹ / L
 - c) Platelets < 100 10⁹ / L
 - d) Hemoglobin < 10 g/dl
 - e) Albumin < 3.5 g

- f) International normalized ratio (INR) > 1.3
- g) Any elevation of bilirubin above normal (unless Gilbert's syndrome or extrahepatic source as denoted by increased indirect bilirubin fraction).
- h) Serum creatinine > 1.5 mg/dl
- i) Creatinine clearance ≤ 50 ml/minute calculated by Crockroft-Gault

20. Pregnancy or breastfeeding.

21. Women, of childbearing age, who are not willing to practice effective contraception (i.e., barrier, oral contraceptives, or past medical history of hysterectomy) for the 48-week duration of the trial and for 1 month after the last administration of the drug. Women with documented (not reported) oophorectomy or hysterectomy are considered sterile. Women with tubal ligation are at small risk and should have pregnancy test at screening.

22. Participation in an investigational drug study within past 30 days.

